8.6 Other assessments

8.6.1 Patient reported outcomes

In this trial a newly developed disease specific PRO - the Hemophilia Treatment Experience Measure (Hemo-TEM) - is being validated. In order to assess the psychometric properties of Hemo-TEM, other questionnaires will be provided; see further [appendix 1](#).

The following ePRO questionnaires are used:

- Haemophilia Treatment Experience Measure (Hemo-TEM)
- Validated Hemophilia Regimen Treatment Adherence Scale – Prophylaxis (VERITAS-Pro®)/Validated Hemophilia Regimen Treatment Scale (/ VERITAS-PRN®)¹⁴
- 36-Item Short Form Health Survey (SF-36v2) (4 week recall)¹⁵
- Patient Global Impression of Change (PGI-C)
- Sheehan Disability Scale (SDS)¹⁶
- Treatment Satisfaction Questionnaire for Medication (TSQM, version II)¹⁷⁻¹⁹
- Haemophilia - Device Assessment Tool (H-DAT)
- Injection Site Reaction Questionnaire (ISRQ) domain of SIAQ (SIAQ-ISRQ)²⁰

The PROs should be assessed at the scheduled visits following the order listed below:

- visit 1 (Hemo-TEM, VERITAS-Pro® or VERITAS-PRN®)
- visit 2 (Hemo-TEM, SF-36v2, SDS, TSQM, SIAQ-ISRQ)
- visit 4 (PGI-C, Hemo-TEM)^a
- visit 5 (PGI-C, Hemo-TEM)
- visit 6 (PGI-C, Hemo-TEM)
- visit 7 (PGI-C, Hemo-TEM)
- visit 8 (PGI-C, Hemo-TEM)
- visit 9 (PGI-C, Hemo-TEM, SF-36v2, SDS, TSQM, H-DAT, SIAQ-ISRQ)
- visit 10 (Hemo-TEM, SF-36v2, SDS, TSQM, SIAQ-ISRQ)
- visit 16 (Hemo-TEM, SF-36v2, SDS, TSQM, H-DAT, SIAQ-ISRQ)

At visit 1 before any visit-related activities all patients should complete Hemo-TEM and VERITAS-Pro® (if the patient at baseline receives prophylactic treatment) / VERITAS-PRN® (if patient at baseline receives on demand treatment).

At visit 2 before any visit-related activities all patients should complete Hemo-TEM, SF36v2, SDS, TSQM and SIAQ-ISRQ.

At visit 4-8: before any visit-related activities the patient should complete the PGI-C before the Hemo-TEM. These are the rules that apply:

Protocol
 Trial ID:NN7415-4255
 UTN:U1111-1179-3872
 EudraCT no.:2016-000614-29

~~CONFIDENTIAL~~

Date:	05 May 2017	Novo Nordisk
Version:	2	
Status:	Final	
Page:	70 of 124	

- If the patient responds “1” to question 1 in the PGI-C, the patient should also complete the Hemo-TEM. In this case the patient should not fill in the PGI-C any more in the trial and the Hemo-TEM only again at visit 9.
- If the patient responds “0” or “2” to question 1 in the PGI-C, the patient should not complete any other questionnaires at this visit, but should repeat the procedure at next visit.

At visit 9 if the patient has responded “0” or “2” in the PGIC at all previous visits, the patient should complete PGI-C. All patients should complete Hemo-TEM, SF-36v2, SDS, TSQM, H-DAT and SIAQ-ISRQ.

At visit 10 all patients should complete Hemo-TEM, SF-36v2, SDS, TSQM and SIAQ-ISRQ.

At visit 16 all patients should complete Hemo-TEM, SF-36v2, SDS, TSQM, H-DAT and SIAQ-ISRQ. The investigator must check the ePROs for potential AEs and SAEs.

The completed ePROs should be transmitted to the ePRO database by the investigator at each visit.

All PROs can be found in [Appendix I](#).

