6.1 Number of patients

Number of patients planned to be screened: 36

Number of patients planned to be started on trial product(s): 33

Number of patients planned to complete the trial: 30

Discontinued patients will not be replaced.

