8.1.9.5 Visit 9 (Assessment visits)

Visit 9 is to be scheduled on trial day 169 (24 weeks) with a visit window of \pm 7days.

Protocol
 Trial ID:NN7415-4255
 UTN:U1111-1179-3872
 EudraCT no.:2016-000614-29

~~CONFIDENTIAL~~

Date:	05 May 2017	Novo Nordisk
Version:	2	
Status:	Final	
Page:	48 of 124	

Treatment with concizumab must take place after the blood sampling at this visit.

Patients will be asked to complete the PRO questionnaires before any other trial related activities are performed according to section [8.6.1](#);

- PGI-C
- Hemo-TEM
- SF-36v2
- SDS
- TSQM
- H-DAT
- SIAQ-ISRQ

Assessments are to be performed according to [Table 2–1](#) and the assessment results from physical examination, concomitant medication, vital signs, Body measurements (weight only) and details of adverse events must be entered into the eCRF.

Investigator is to perform compliance check of treatment and reporting of bleeding episodes through the available access to collected data from the eDiary. Based on the assessment of any spontaneous bleeding episodes the investigator must evaluate if an escalation of the concizumab doses is needed according the escalation rules described in section [5.3.1](#). All decisions to escalate the concizumab dose must be recorded in the eCRF.

The patient will be asked to return all used, partly used and unused concizumab cartridges and turoctocog alfa (FVIII) during the trial as instructed by the investigator. Drug accountability must be performed at all visits for concizumab and rFVIII (turoctocog alfa) including injection kits, if applicable.

In order to determine the correct amount of the patient's daily dose of concizumab, until next scheduled visit, investigator will consult the dosing-table in the TMM on basis of the patient's current body weight. Investigator will communicate any corrections in the daily dose of concizumab to the patient and record the dose for the coming home treatment period in the eCRF.

A dispensing call must be performed in the IWRS.

At the visit the patient will be provided with trial product (concizumab and if necessary rFVIII (turoctocog alfa)) and injection kits to be able to conduct home treatment until next scheduled visit.

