17.7.2 Exploratory patient reported outcome endpoints

- Change in Hemo-TEM after 24 weeks from treatment onset
- Change in Hemo-TEM after 76 weeks from treatment onset
- Change in VERITAS-Pro®/VERITAS-PRN® after 24 weeks from treatment onset
- Change in VERITAS-Pro®/VERITAS-PRN® after 76 weeks from treatment onset

Protocol
 Trial ID:NN7415-4255
 UTN:U1111-1179-3872
 EudraCT no.:2016-000614-29

~~CONFIDENTIAL~~

Date:
 Version:
 Status:
 Page:

05 May 2017 | **Novo Nordisk**
 2
 Final
 105 of 124

- Change in SF-36v2 after 24 weeks from treatment onset
- Change in SF-36v2 after 76 weeks from treatment onset
- Change in SDS after 24 weeks from treatment onset
- Change in SDS after 76 weeks from treatment onset
- Change in TSQM after 24 weeks from treatment onset
- Change in TSQM after 76 weeks from treatment onset
- Change in SIAQ-ISRQ after 24 weeks from treatment onset
- Change in SIAQ-ISRQ after 76 weeks from treatment onset
- Change in PGI-C after 24 weeks from treatment onset
- Change in PGI-C after 76 weeks from treatment onset
- Change in H-DAT after 24 weeks from treatment onset
- Change in H-DAT after 76 weeks from treatment onset
-

Patient reported outcomes (PROs) will be collected using questionnaires at visits 1, 2, 4, 5, 6, 7, 8, 9, 10 and 16.

Patient reported outcome questionnaires to be analysed:

- Haemophilia Treatment Experience Measure (Hemo-TEM)
- Validated Hemophilia Regimen Treatment Adherence Scale – Prophylaxis (VERITAS-Pro[®]) or Validated Hemophilia Regimen Treatment Scale (/ VERITAS-PRN[®])¹⁴
- 36-Item Short Form Health Survey (SF-36v2) (4 week recall)¹⁵
- Patient Global Impression of Change (PGI-C)
- Sheehan Disability Scale (SDS)¹⁶
- Treatment Satisfaction Questionnaire for Medication (TSQM, version II)¹⁷⁻¹⁹
- Haemophilia - Device Assessment Tool (H-DAT)
- Injection Site Reaction Questionnaire (ISRQ) domain of SIAQ (SIAQ-ISRQ)²⁰

Protocol
 Trial ID:NN7415-4255
 UTN:U1111-1179-3872
 EudraCT no.:2016-000614-29

~~CONFIDENTIAL~~

Date: 05 May 2017
 Version: 2
 Status: Final
 Page: 106 of 124

Novo Nordisk

VERITAS-Pro[®] or VERITAS-PRN[®], SF-36v2, SDS, TSQM, H-DAT and SIAQ-ISRQ will be scored according to their respective scoring algorithms. Change from visit 2 to visit 9 and change from visit 2 to visit 16 will be described.

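### The 24-week PGI-C endpoint is stated for everyone, but Section 8.6.1 collects PGI-C at visit 9 only from patients who never answered 1 at visits 4 to 8

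*Protocol*

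**What the plan says.** References are to protocol version 2; version 1 has the same wording on this point.

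- **Stop rule (8.6.1, visits 4 to 8).** A patient who answers 1 to question 1 of the PGI-C also completes the Hemo-TEM at that visit. Then: "In this case the patient should not fill in the PGI-C any more in the trial and the Hemo-TEM only again at visit 9". A patient who answers 0 or 2 completes nothing else at that visit and is asked again at the next one.
- **Visit 9 condition (8.6.1).** If the patient has answered 0 or 2 "in the PGIC at all previous visits, the patient should complete PGI-C". The next sentence covers everyone and leaves PGI-C out: "All patients should complete Hemo-TEM, SF-36v2, SDS, TSQM, H-DAT and SIAQ-ISRQ".
- **Timing (8.1.9.5).** "Visit 9 is to be scheduled on trial day 169 (24 weeks"), so visit 9 is the 24-week assessment.
- **Endpoint (4.2.3.2 and 17.7.2).** "Change in PGI-C after 24 weeks from treatment onset", with no restriction to a subset. Section 17.7.2 also names PGI-C among the questionnaires to be analysed.
- **Visit lists.** The list in 8.6.1 has "visit 9 (PGI-C, Hemo-TEM, SF-36v2, SDS, TSQM, H-DAT, SIAQ-ISRQ") with no condition attached. Section 8.1.9.5 also lists PGI-C, introduced by "Patients will be asked to complete the PRO questionnaires before any other trial related activities are performed according to section" 8.6.1.

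**The concern.** The endpoint wording promises a 24-week result for the trial population. The collection rule delivers a week-24 answer only for patients who passed a filter built from their own earlier answers to the same item. The missing values are created by design and depend on the outcome.

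A tabulation of visit 9 PGI-C would thus describe a selected group, and a reader of the report could take it for the impression of change among all patients at week 24. No analysis plan can repair this for current status, because answers that were never requested cannot be recovered.

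An older answer is a weak substitute. Under 5.3.1 and 8.1.9.4, dose escalation is assessed at visits 4 to 8, so a patient may be on a different dose at week 24 from the one he was on when he answered 1.

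**Working it through.** The protocol gives no figure for PGI-C, so there is nothing to reproduce. The check is first on the text and then on scale.

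**Step 1: what each patient has at week 24 under 8.6.1, if visits are attended**

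| Answers at visits 4 to 8 | PGI-C asked at visit 9? | PGI-C information available |
|---|---|---|
| 0 or 2 every time | Yes | Current answer at week 24 |
| 1 at some visit | No | One dated answer of 1, nothing later |

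The endpoint in 4.2.3.2 and 17.7.2 makes no distinction between these rows.

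**Step 2: age of the earlier answer**

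Scheduled days are 29 for visit 4 and 141 for visit 8 (8.1.9.4), and 169 for visit 9 (8.1.9.5).

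- First answer of 1 at visit 4: 169 − 29 = 140 days = 20 weeks old.
- First answer of 1 at visit 8: 169 − 141 = 28 days = 4 weeks old.

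These ages are before allowing for the 7-day visit windows.

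**Step 3: how many patients might be affected**

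The documents do not give the chance of answering 1. Assume a constant chance p at each of the five visits 4 to 8, independent across visits. The share not asked at visit 9 is then 1 − (1 − p)^5. Section 6.1 plans 33 patients started and 30 completing.

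| p | (1 − p)^5, still asked | Share not asked | Still asked, of 33 | Still asked, of 30 |
|---|---|---|---|---|
| 0.05 | 0.774 | 23% | 25.5 | 23.2 |
| 0.10 | 0.590 | 41% | 19.5 | 17.7 |
| 0.20 | 0.328 | 67% | 10.8 | 9.8 |
| 0.30 | 0.168 | 83% | 5.5 | 5.0 |

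Of 30 completers, the number not asked is 30 − 17.7 = 12.3 at p = 0.10, 30 − 9.8 = 20.2 at p = 0.20, and 30 − 5.0 = 25.0 at p = 0.30.

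**Step 4: how far independence drives this**

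One patient's repeated answers are likely to be alike. In the extreme case where each patient would give the same answer at every visit, the share who ever answer 1 is p itself: 10%, 20% and 30% for p = 0.1, 0.2 and 0.3. For a given p, positively related answers put the share between p and 1 − (1 − p)^5. The table is therefore an indication of scale and not a prediction.

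**The case against.** **What stands against the point.** Patients who answered 1 are not without data. Each has that answer at a known visit, with a Hemo-TEM at the same visit and another at visit 9. If visits are attended, whether a patient ever answered 1 by week 24 can be determined for everyone. The rule also looks deliberate: 8.6.1 says that the Hemo-TEM is being validated in this trial, and pairing it with the first answer of 1 fits such a purpose. The endpoint is exploratory and carries no test. All of this stands and limits the weight of the point. It does not supply current status at week 24, and it does not explain skipping PGI-C at visit 9, where every patient completes the Hemo-TEM anyway.

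**Stronger readings that a reader might infer, and that the documents do not support:**

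- *That 8.6.1 contradicts the visit 9 schedule.* Section 8.1.9.5 does not say that all patients complete PGI-C, and it refers to 8.6.1, where the condition sits. Section 8.1.9.4 likewise lists PGI-C and Hemo-TEM for visits 4 to 8 without a condition, although 8.6.1 makes them conditional there. The lists read as menus.
- *That the anchor for Hemo-TEM change at visit 9 is lost.* No section gives PGI-C that role. Section 8.6.1 says only that the other questionnaires serve to assess the psychometric properties of the Hemo-TEM.
- *That a scoring rule is missing.* The scoring sentence in 17.7.2 does not name PGI-C, but such a rule may properly sit in the statistical analysis plan, which is not shown.
- *That the visit 9 result is biased by a known amount or in a known direction.* The meaning of 0, 1 and 2 is in an appendix that is not shown, and no response pattern is given.

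**Conclusion.** The point holds as a mismatch between an endpoint and its data collection. As 8.6.1 is written, the 24-week PGI-C endpoint cannot describe current status at week 24 in the treated population, because patients who answered 1 at visits 4 to 8 are never asked again and the visit 9 values come from those who never gave that answer.

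The existence of the selection follows from the text alone. Its extent does not: the 41% to 83% not asked rests on an assumed p of 0.1 to 0.3 and on independence between visits, and the share would be smaller if each patient's answers tend to repeat. Its direction cannot be stated. The consequence is confined to one exploratory endpoint; the primary analysis and the safety endpoints are untouched. The change is worth making because it is cheap and because unasked answers cannot be recovered later.

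**What to change.** **Preferred.** Change two places in 8.6.1: the stop rule for visits 4 to 8, so that it no longer runs to the end of the trial, and the visit 9 condition, so that all patients complete PGI-C at visit 9 whatever they answered before. Keep the conditional rule for visits 4 to 8. The Hemo-TEM pairing at the first answer of 1 is preserved.

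The cost is two edited sentences, the matching ePRO setting, and one extra questionnaire for patients who answered 1 earlier, at a visit where they already complete six others.

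**If the sponsor keeps the current rule.** Redefine the 24-week PGI-C endpoint in 4.2.3.2 and 17.7.2 as first answer of 1 by visit 9, which the collected data can support. This needs no new data collection, but it gives up any statement about current status at week 24.

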8.6.2 Training

The patients must be trained in how to handle bleeding episodes and how to recognize the signs and symptoms of thrombosis. The training must be recorded in the medical records.

8.6.2.1 Concizumab and NovoPen[®] 4

A direction for use (DFU) will be available as hand out for patients at visit 2. Training in NovoPen[®] 4 can start at screening (visit 1) and s.c. administration of concizumab using the NovoPen[®] 4 can start at the first dose at the trial site (visit 2). Patients must be instructed that injections are to be performed subcutaneously, not intravenously. Concizumab and NovoPen[®] 4 will be dispensed to patients at visit 2. Training must be performed at site until patients feel comfortable using the device or performing the treatment. The training must be documented in the medical records.

Detailed instructions can be found in the DFU.

8.6.2.2 Turoctocog alfa

A direction for use (DFU) will be available as hand out for patients at visit 1. Training must be performed at site until patients feel comfortable performing the treatment. The training must be documented in the medical records.

Detailed instructions can be found in the DFU.

Protocol
Trial ID:NN7415-4255
UTN:U1111-1179-3872
EudraCT no.:2016-000614-29

~~CONFIDENTIAL~~

Date:	05 May 2017	Novo Nordisk
Version:	2	
Status:	Final	
Page:	71 of 124	

8.6.2.3 eDiary

Training on the use of the eDiary can start at visit 1. The eDiary will be provided to the patients at visit 2.

Training must be repeated at the site until patients feel comfortable using the device. The training must be documented in the medical records.

During the home treatment period the patient must ensure that all home treatments of concizumab, details of bleeding episodes and the turoctocog alfa (FVIII) treatment associated with these bleeding episodes are captured in the eDiary as instructed and trained by investigator or delegated staff.

It will be the responsibility of the investigator or delegated staff to assess the eDiary data throughout the conduct of the trial and to ensure data entry compliance (timely entry, no duplicates data, no missing data etc.) and retraining if necessary.

For patients completing the trial or in case of withdrawal, the eDiary will be collected at the end of trial.

8.6.3 Surgery

Minor surgery can be performed within this trial at the investigator's discretion according to local guidelines. Definition of minor surgery, see section [5.1.1](#). Major surgery is not allowed, see exclusion criteria no [6](#).

For minor surgery the following should be recorded in the eCRF:

- Date, stop time and dose of preventive treatment with turoctocog alfa before surgery, if this was deemed necessary by the investigator
- Indication for surgery
- Location of surgery
- Date of surgery
- Start and stop time of surgery

8.7 Patient compliance

Throughout the trial, the investigator will remind the patients to follow the trial procedures and requirements to ensure patient compliance. If a patient is found to be non-compliant, the investigator will remind the patient in the importance of following the instructions given including taking the trial products as prescribed.

Assessment of patient compliance with protocol procedures for determination of continuation of the trial will be done by the investigator on an ongoing basis.

Protocol
Trial ID:NN7415-4255
UTN:U1111-1179-3872
EudraCT no.:2016-000614-29

~~CONFIDENTIAL~~

Date:	05 May 2017	Novo Nordisk
Version:	2	
Status:	Final	
Page:	72 of 124	

8.8 Treatment compliance:

Treatment compliance will be monitored and documented through timely review of eDiary data and drug accountability.

Concizumab will be administered at the trial site at visit 2 supervised by medically trained trial staff and administration at home can be initiated after visit 2 if the patient feels comfortable with the s.c. administration. Administration of turoctocog alfa (rFVIII) for bleeding episodes will be administered at the trial site by a medically trained trial staff or at home by the patient, see section [8.3.1](#).

The patient will be asked to return all used, partly used and unused trial product during the trial as instructed by the investigator. Drug accountability will be performed and will be used to assess patient compliance together with the patient's adherence to trial procedures.

Compliance check includes a cross check between records in EDC/eDiary (number of administrations and bleeding episodes) and the used/returned cartridges/vials.

Protocol
 Trial ID:NN7415-4255
 UTN:U1111-1179-3872
 EudraCT no.:2016-000614-29

~~CONFIDENTIAL~~

Date: 05 May 2017
 Version: 2
 Status: Final
 Page: 73 of 124

Novo Nordisk

9 Trial supplies

Trial supplies comprise trial products and auxiliary supplies. Additional details regarding trial supplies can be found in the Trial Materials Manual (TMM).

The trial product, concizumab B, appears clear to slightly opalescent and colourless to slightly yellow. The trial product must not be used if it contains visible particles or discoloration.

The reconstituted turoctocog alfa (FVIII) solution appears as a clear or slightly opalescent solution. Do not use the reconstituted solution if it has visible particles or discoloration.

Trial products must not be dispensed to any person not included in the trial.

9.1 Trial products

The following trial products will be provided by Novo Nordisk, Denmark:

Table 9–1 Trial products

Trial product	Strength	Dosage form	Route of administration	Container/delivery device
concizumab B (IMP ^a)	100 mg/mL	Solution for injection	s.c. injection	3 ml cartridge
turoctocog alfa (NIMP ^b)	2000 IU/vial	Powder for solution for injection	i.v. injection	Vial
0.9% Sodium Chloride Solution (NIMP ^b)	N/A	Solvent for solution for injection	i.v. injection	4 ml prefilled syringe

^a Investigational Medicinal Product (IMP)

^b Non-Investigational Medical Product (NIMP) given as NIMP for bleeding episodes

The NovoPen[®]4 injector will be supplied by Novo Nordisk and used for the s.c. administration of concizumab. NovoPen[®]4 will be labelled in accordance with the EMA directive on medical devices annex I²¹ and similar national legislation. A description on how to use the device is given in the DFU.

9.2 Labelling

The trial products will be labelled in accordance with Annex 13²², local regulations and trial requirements.

Protocol
 Trial ID: NN7415-4255
 UTN: U1111-1179-3872
 EudraCT no.: 2016-000614-29

~~CONFIDENTIAL~~

Date: 05 May 2017 | **Novo Nordisk**
 Version: 2
 Status: Final
 Page: 74 of 124

Each trial site will be supplied with sufficient trial products for the trial on an on-going basis controlled by the IWRS. Trial products will be distributed to the trial sites according to enrolment and drug dispensing of distribution.

The investigator must document that direction for use is given to the patient orally and in writing at the first dispensing visit (see flow chart section 2).

9.3 Storage

Table 9–2 Storage conditions

Trial product	Storage conditions (not-in-use)	In-use conditions	In-use time ^a
concizumab B 100 mg/mL	Store in refrigerator (2°-8°C) Do not freeze Protect from light	Store at room temperature (below 30°C) Do not refrigerate Protect from light	Use within 4 weeks (28 days)
turoctocog alfa 2000 IU/vial	Store in refrigerator (2°-8°C) Do not freeze Protect from light May be stored at room temperature (9-30°C) for a single period not exceeding 9 months. Do not return the product to the refrigerator. Write the start date for the storage at room temperature on the label	For single use To be used immediately after reconstitution Use within 4 hours after reconstitution when stored at room temperature	N/A
0.9% sodium chloride solution	Store at 2°-30°C Do not freeze Protect from light	For single use	N/A

^a In-use time for concizumab starts when first dose is administrated from an individual cartridge and for turoctocog alfa when the product is reconstituted

The investigator must ensure that trial product is kept under proper storage conditions and record and evaluate the temperature. The investigator must inform Novo Nordisk **immediately** if any trial product has been stored outside specified conditions (e.g. outside temperature range). Additional details regarding handling of temperature deviations can be found in the TMM.

Trial product that has been stored improperly must not be dispensed to any patient before it has been evaluated and approved for further use by Novo Nordisk. The investigator must take appropriate action to ensure correct storage.

Protocol
 Trial ID:NN7415-4255
 UTN:U1111-1179-3872
 EudraCT no.:2016-000614-29

~~CONFIDENTIAL~~

Date:	05 May 2017	Novo Nordisk
Version:	2	
Status:	Final	
Page:	75 of 124	

Investigator must instruct the patient to use and store trial product according to the label.

